### **3.1f Analytic Plan**

**Assessing intervention efficacy in reducing emergency department (ED) presentation for an overdose or overdose death (Aim 1, secondary endpoint).** First, we will compare the overall rate of patients experiencing this composite outcome over the 12-month follow-up period in each group. Next, we will examine the time to first ED presentation or death using a Kaplan-Meier analysis. Patients will be censored as of the first date of either of these outcomes or at the end of the 12-month period. We will use Breslow's method to test if the time to either outcome differs between the groups, since this approach gives greater emphasis to shorter time elapsed after the intervention, which has greater clinical significance. Third, Cox proportional hazards modeling will be used to estimate hazard ratios for the treatment effect. Multivariable models will be constructed to adjust for possible post-randomization confounding.

**Examine whether the treatment effect is mediated by differential uptake of risk reduction behaviors in the intervention arm (Aim 2).** If the RAPIDS intervention shows efficacy in reducing overdose rates among the sample (Aim 1), we will explore the extent to which this relationship works through several possible mediators (see Figure 4). For mediation analyses, first, we will examine, in multivariable regression models, which mediators, if any, are significantly changed by the intervention (i.e., the rate of change differed by treatment

---

 <https://rc.partners.org/research-apps-and-services/collect-data#redcap>

Brown University IRB Original Approval: 4/18/2019  
Brown University IRB Amendment Approval: 11/22/2019  
Brown University IRB Amendment Approval: 8/10/2020  
Brown University IRB Amendment Approval: 10/15/2020  
Brown University IRB Amendment Approval: 02/26/2021  
Brown University IRB Continuing Review Approval: 03/18/2021  
Brown University IRB Amendment Approval: 06/15/2021  
Brown University IRB Amendment Approval: 09/01/2021  
Brown University IRB Amendment Approval: 10/05/2021  
Brown University IRB Amendment Approval: 11/09/2021  
Brown University IRB Amendment Approval: 12/13/2021

assignment). For those that are significantly impacted by the intervention, we will conduct path analysis using structural equation modeling to determine whether the effect of the intervention on overdose is through the hypothesized mediator(s). Structural equation modeling (SEM) allows for the simultaneous estimation of total, direct, mediated and indirect effects of a causal variable (i.e., the intervention) on the outcome (i.e., overdose) through a set of mediator variables. SEM can handle outcomes and mediators with a variety of distributions (including, Gaussian, Poisson and Binomial). Inferences for indirect effects can be estimated using bootstrapped confidence intervals.

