#### **Data Entry Methods**

Survey data will be collected on password-protected tablets and computers within the Centers for Epidemiology and Environmental Health (CEEH) at the Brown University School of Public Health. The REDCap™ platform exceeds patient confidentiality and data security requirements for clinical trials, and are both HIPAA compliant and fully validated for FDA 21 CFR Part 11.

The project's Biostatistician will manage the REDCap™ database architecture, dataset storage, and all input/output (i.e., data transfer) regulations.

Brown University IRB Original Approval: 4/18/2019  
Brown University IRB Amendment Approval: 11/22/2019  
Brown University IRB Amendment Approval: 8/10/2020  
Brown University IRB Amendment Approval: 10/15/2020  
Brown University IRB Amendment Approval: 02/26/2021  
Brown University IRB Continuing Review Approval: 03/18/2021  
Brown University IRB Amendment Approval: 06/15/2021  
Brown University IRB Amendment Approval: 09/01/2021  
Brown University IRB Amendment Approval: 10/05/2021

Brown University IRB Amendment Approval: 11/09/2021  
Brown University IRB Amendment Approval: 12/13/2021

For all analyses, a series of routine procedures will first be conducted to ensure data accuracy/adequacy. Descriptive statistics will provide examination of the variables' distributional properties; if required, data will be transformed to achieve normality. For all analyses, we will adopt an intention-to-treat (ITT) approach to address potential problems inherent in following only intervention completers (e.g., self-selection effects, differential attrition across groups). Prior to examining intervention effects, we will first assess the success of randomization on pre-intervention characteristics using one-way analysis of variance (ANOVA), with intervention group as the predictor variable. The extent to which groups differ on baseline characteristics will determine whether any of these should be included as covariates in the primary analyses (see below). Missing covariate data will be handled using multiple imputation performed in two stages using chained equations that specify the conditional models for all of the variables with missing values.

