#### **Assessing intervention efficacy in reducing self-reported overdose (Aim 1, primary endpoint).**

First, in the ITT analysis, we will determine the efficacy of the intervention by comparing self-reported rates of overdose among those assigned to the intervention arm versus the control group. First, we will use logistic regression to determine the independent effect of the intervention on the proportion reporting an overdose over the follow-up period, adjusting for baseline covariates as needed. Second, we will use generalized linear mixed effects models (GLMMs) with a logit link function to examine differences in self-reported overdose rates at each time point by incorporating fixed effects representing time, an intervention assignment indicator, and an interaction term that assesses the significance of the intervention influence over time. Third, in a per-protocol sub-analysis, we will determine the effect of the intervention on self-reported overdoses among those who used the fentanyl test strips.

Per-protocol analyses will be based on principal stratification. Principal stratification is a statistical technique that is used to adjust for a post-treatment variable (e.g., utilization of fentanyl test strips), and treatment effects are estimated within each stratum of that variable. We can then estimate the effect of the intervention in reducing rates of self-reported overdoses, conditional on whether participants used the test strips.

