#### Assessing intervention efficacy in reducing fatal and nonfatal overdose (Aim 1, primary endpoint).

The primary outcome will be **non-fatal overdose**, defined as a composite outcome, consisting of one of the following:

1. A self-reported overdose ascertained at the six and/or 12 month follow-up visits;
2. A non-fatal opioid overdose identified in the Rhode Island EMS database, using a case definition for suspected overdose developed by RIDOH previously;
3. An emergency department encounter for an accidental drug overdose that did not result in death, using a case definition developed by the CDC;

The primary analysis will be conducted using a survival framework, with time to *first* nonfatal overdose—identified through any of the data sources noted above—serving as the primary outcome. For self-reported data, event times will be estimated from SAE reports (in which participants are asked to estimate the date of their overdose). Participants will be right-censored as of the date of the first

---

 <https://www.ncbi.nlm.nih.gov/pmc/articles/PMC7948191/>

outcome event or at the end of the follow-up period, defined as 15 months following the participant's baseline visit.

To account for potential imbalance and to improve statistical efficiency, we will adjust for known or anticipated prognostic variables measured at baseline. These variables will include sociodemographic characteristics (e.g., age, gender identity, race/ethnicity), recent criminal justice involvement, housing instability, and substance use patterns including injection drug use & history of overdose. Variables will be transformed or categorized as necessary to address skewed or imbalanced data. We will also adjust for pre-baseline EMS runs for suspected opioid overdoses and ED encounters for drug overdoses using the case definitions noted above, occurring up to six months prior to the date of the participant's baseline visit.

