At the completion of the study, patterns of data missingness will be explored to determine the appropriate assumptions required for each affected variable. Missing covariate data considered to be missing completely at random (MCAR), missing at random (MAR) and/or missing not at random (MNAR) will be handled using multiple imputation in SAS (proc MI procedure). Performed in two stages using chained equations, the model will specify the conditional models for the missing outcome and covariates as "MCAR", "MAR", or "MNAR". First, missing patterns will be tested. Then, imputing procedures will be separated into an "imputation phase", "analysis phase" and a "pooling phase". Finally, models with complete case, available data, and fully imputed data will be compared based on their coefficients, standard errors (SE), and *p*-value for the covariates included in the model.

To examine the effect of missing self-reported outcome data on the results, we will first examine the concordance between the self-reported outcome and the primary endpoints relying on administrative data linkages. If a high degree of correlation is observed (e.g.,  $r > 0.80$ ), we will assume missing self-reported outcome information has a negligible impact on the results. If a lack of concordance is observed, we will conduct stratified analyses by number of completed outcome visits (e.g., zero, one, and two) and also employ imputation-based procedures as noted above.

Second, in an exploratory analysis, we will determine the effect of the intervention on the more severe overdose endpoints, defined as an EMS run for suspected overdose, an ED encounter for drug overdose, or drug overdose death. An unintentional fatal overdose (involving any substance) will be determined through linkage to the Office of the State Medical Examiner (OSME), which is responsible for investigating all accidental deaths. Specifically, as defined previously, cases will be considered confirmed unintentional drug-related overdose fatalities if: (i) the death was pronounced in Rhode Island; (ii) the final manner of death was deemed an accident by the medical

---

 <https://doi.org/10.1016/j.drugpo.2017.05.029>

examiner, and (iii) a drug is listed on the death certificate as the primary cause of death or a significant contributing factor. This analysis will be conducted using the same methodology as described above.

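### The protocol's adjusted Cox model for ED visits or overdose death may condition on post-randomisation variables, and its covariate rules disagree with the SAP's baseline adjustment

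*Protocol*

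**What the plan says.** Three texts govern covariate adjustment, and they do not agree.

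- **Protocol 3.1f, Aim 1 secondary endpoint.** After a comparison of rates, a Kaplan-Meier analysis, a Breslow test and a Cox hazard ratio comes the sentence: "Multivariable models will be constructed to adjust for possible post-randomization confounding". No variables are named, and nothing limits the models to baseline data.
- **Protocol, Data and Safety Monitoring Plan, section C1.** Randomisation is checked on pre-intervention characteristics "using one-way analysis of variance (ANOVA), with intervention group as the predictor variable", and then: "The extent to which groups differ on baseline characteristics will determine whether any of these should be included as covariates in the primary analyses". No threshold is given. The primary logistic model is described as "adjusting for baseline covariates as needed".
- **SAP section 3, Aim 1.** The rule carries no condition: "we will adjust for known or anticipated prognostic variables measured at baseline". Overdose events in EMS and ED records in the six months before baseline are added. The list is indicative: "These variables will include sociodemographic characteristics (e.g., age, gender identity, race/ethnicity), recent criminal justice involvement, housing instability, and substance use patterns", with injection use and overdose history. Coding is left open: "Variables will be transformed or categorized as necessary to address skewed or imbalanced data". For the exploratory severe endpoint (EMS run, ED encounter or overdose death): "This analysis will be conducted using the same methodology as described above".

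Neither document says that the protocol's wording is withdrawn or which text governs.

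**The concern.** In a randomised comparison, nothing that happens after allocation can confound allocation. A variable measured later can lie on the path from intervention to overdose, or share causes with overdose, or both. Adjusting for it removes part of the effect in the first case and can create an association in the second.

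That is a concrete risk here. Protocol 3.1b names test strip use as a mediator and lists discarding contaminated drugs, not using alone and keeping naloxone nearby as target behaviours, asked about at each visit. Aim 2 analyses uptake of risk reduction behaviours as mediation. Treating the same variables as confounders in Aim 1 contradicts that model and the intention-to-treat approach that both documents adopt for all analyses.

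The imbalance rule is a different and lesser problem. It concerns baseline variables only, but it leaves the primary model to be chosen after the data are seen. Prespecification matters more than usual in this trial, because SAP section 5 says that self-reported overdoses are unblinded to the biostatistician and principal investigator as they are reported.

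**Working it through.** **1. Design inputs.** The plan gives no figure for this point, so the check starts with the design values used below. The power section assumes 500 enrolled and 80% retention (200 evaluable per arm), with 20% against 10% experiencing an overdose, and states more than 80% power. With pooled proportion 0.15, the null standard error is √(2 × 0.15 × 0.85 / 200) = 0.0357. The alternative standard error is √((0.20 × 0.80 + 0.10 × 0.90) / 200) = 0.0354. Then z = (0.10 − 1.96 × 0.0357) / 0.0354 = 0.85, and power is 80.2%. The stated figure reproduces.

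**2. Loss of mediated effect.** If a share *m* of the log hazard ratio runs through the adjusted variables, then approximately log HR(adjusted) = (1 − *m*) × log HR(total). With HR(total) = 0.50, the plan's design effect, ln 0.50 = −0.693.

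| Assumed share *m* | Adjusted log HR | Reported HR |
|---|---|---|
| 0 | −0.693 | 0.50 |
| 0.50 | −0.347 | 0.71 |
| 0.75 | −0.173 | 0.84 |
| 1 | 0 | 1.00 |

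The documents give no value for *m*.

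**3. Simulation of the adjustment rules.** There were 400 evaluable participants, one year of follow-up and 2,500 runs per scenario. From the documents: 37% have a baseline prognostic factor (lifetime overdose in the pilot); 77% of the intervention arm take up the behaviour (pilot strip use among those who returned); and the control hazard is either 0.223 per year (−ln 0.80, about 20% risk) or 0.08 per year (8 per 100 person-years, the secondary-endpoint assumption). Assumed, not in the documents: HR 3 for the baseline factor, 10% uptake in controls and HR 0.32 for the behaviour. In the shared-cause scenario, the behaviour has log odds −2 + 3 × arm + U, where U is an unmeasured standard normal variable that raises the log hazard of overdose by 0.8 per unit.

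| Scenario | Model | HR, about 20% risk | HR, 8 per 100 person-years |
|---|---|---|---|
| Whole effect runs through the behaviour | Unadjusted | 0.50 | 0.49 |
| | Adding the behaviour | 0.98 | 0.94 |
| No effect; behaviour and overdose share a cause | Unadjusted | 0.99 (type I error 4.2%) | 1.00 (4.6%) |
| | Adding the behaviour | 0.70 (23.8%) | 0.70 (12.3%) |

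The shared-cause bias runs in the intervention's favour because U was given the same sign for uptake and for overdose. With opposite signs it would run the other way.

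**4. Choosing a baseline covariate by imbalance** (kept only if the arms differ at p < 0.05), with the same baseline factor and no post-randomisation variable:

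| Scenario | Rule | HR, about 20% risk | Tests rejecting | HR, 8 per 100 person-years | Tests rejecting |
|---|---|---|---|---|---|
| True HR 0.50 | Always adjust | 0.49 | 73.4% | 0.48 | 33.7% |
| | Adjust if imbalanced | 0.50 | 71.4% | 0.48 | 32.6% |
| No effect | Always adjust | 1.00 | 4.7% | 1.00 | 4.6% |
| | Adjust if imbalanced | 1.00 | 4.8% | 1.00 | 4.6% |

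Across the null scenarios at about 20% risk, including the one in step 3, selection gives a type I error of 4.2% to 4.8%. The cost is about one to two points of power for a single covariate of this strength.

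**The case against.** The strongest reply is that the sentence in 3.1f names no variables and may mean chance imbalance left after randomisation. The monitoring plan ties covariates to how well randomisation worked, and the SAP adjusts partly for potential imbalance. On that reading nothing measured after baseline enters the model and there is no bias. The documents do not settle the meaning. Elsewhere, however, they use the term for time after allocation: in Protocol 3.1a, monitoring plan section A1 and SAP section 1, visits are dated in months post-randomization. The literal reading is therefore the natural one. Even the benign reading leaves an open-ended rule at odds with the SAP.

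The second reply is that the SAP is more specific and appears later: a footnote link dates from 2022, while the last protocol approval shown is December 2021. It replaces the protocol's logistic and mixed models with a time-to-event analysis, makes the severe endpoint exploratory and gives that endpoint the same methodology. Analysts would probably follow it. This limits the practical risk but does not remove it. Nothing states that the SAP governs, and its severe endpoint adds EMS runs, so it does not restate the protocol's two-part composite.

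The third reply is about scope. The sentence covers only the multivariable models. The rate comparison, Kaplan-Meier analysis, Breslow test and Cox hazard ratio listed before it remain randomised comparisons. That stands.

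**Conclusion.** The point holds in a limited form. If post-baseline behaviours are entered in the Cox model of Protocol 3.1f, its hazard ratio does not estimate the intention-to-treat effect. A hazard ratio of 0.50 could be reported anywhere from close to 0.50 to close to 1, with 0.71 if half of the log hazard ratio is mediated. A shared cause could instead produce an apparent effect where there is none. These figures rest on assumed mediated shares, uptake and shared-cause strength; they illustrate the risk and do not predict this trial's result.

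Three stronger conclusions might be inferred and are not supported:

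- That the primary analysis is biased by post-randomisation adjustment. The sentence belongs to one adjusted analysis of a secondary endpoint, and the primary models in both documents use baseline covariates.
- That choosing baseline covariates by imbalance biases the effect. It does not do so materially; its faults are lack of prespecification, some lost efficiency and disagreement with the SAP.
- That the SAP's covariate set is already fixed. It is limited to baseline variables and does not depend on imbalance, but its membership is open and its coding depends on the data.

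The texts should be reconciled before the analysis.

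**What to change.** - In Protocol 3.1f, replace the sentence with adjustment for prespecified baseline covariates only.
- In section C1 of the monitoring plan, delete the rule that observed differences choose the covariates, and remove 'as needed' from the primary model. The baseline table can stay as description.
- In both documents, state that the intention-to-treat primary and severe-endpoint models use one closed list of baseline covariates, built from the SAP's list, with the coding of each fixed in advance and applied whatever imbalance is seen.
- Say which document governs where they differ.
- Do not extend the baseline-only rule to every efficacy analysis. The mediation, principal-stratification, per-protocol and instrumental-variable analyses use post-randomisation data by design and should stay as separately labelled analyses.

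The cost is a short text amendment and one covariate table. No new data are needed and the sample size does not change. Because overdose reports are seen unblinded as they arrive, the list and coding should be settled without reference to outcomes by arm.

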#### **Determine whether intervention efficacy varies across participant subgroups (Aim 3).**

We will examine if heterogeneity of intervention effect is modified by key baseline characteristics of interest, including: age; sex; type, frequency, and route of drug use; baseline level of overdose risk (e.g., lifetime history of overdose); and pre-intervention motivations for fentanyl test strip utilization. We will perform stratified subgroup analyses to determine if treatment effects vary between groups of individuals.

#### **3.1 g COVID-19 procedures and precautions**

In response to the COVID-19 pandemic, a number of cleaning, social distancing, and contact tracing procedures are being implemented. These procedures are discussed in detail in Attachment J, Reopening Plan. In short, research staff will take extensive measures to clean the study space at the beginning of each day, between participants and at the end of each day. Research staff and participants and staff will wear masks and maintain adequate distance from each other when a door cannot be closed between them. The only time participants and staff will be closer than 6 feet from each other is for the collection of the dried blood spot. The finger prick will take a matter of minutes, and during that time, the research staff will wear a face shield.

On the day prior to a study visit and on the day of, participants will be screened for COVID exposure and risk. During the visits, surveys will be conducted over zoom with participants and staff sitting in nearby, but separate rooms. This will ensure that staff and participants are not in a closed space for longer than necessary.

Contact tracing logs will be kept and maintained in REDCap. In the event of participant or staff COVID exposure, the research team follow Rhode Island Department of Health contact tracing procedures.

We recognize that as guidance changes, safety procedures may have to be modified. At any point, if Brown University issues additional guidelines, the staff will follow those procedures in addition to or in place of the guidelines proposed on **Attachment J**.

#### **3.2 Informed Consent Procedure**

We will obtain verbal informed consent from participants at the start of the Screening process, and e-signed informed consent for the interviewer-administered surveys at the Baseline enrollment visit (see **Attachment A** for consent forms). Participants will be asked if they would like a copy of the consent form emailed to them. The enrollment consent form will be reviewed with the subject in a quiet, private location at the Brown University School of Public Health at the start of the Baseline Visit. All participants will be given detailed explanations of their rights as human subjects, including the purpose of the study, length of time for the interview process, study requirements, and risks and benefits of the interventions.

Participants who refuse consent to participate, are unable to provide informed consent due to altered mental status, or who cannot adequately hear and/or comprehend either consent process, will not be enrolled.

Participants will be asked to sign electronic copies of completed consent forms that will be stored in the Stronghold Environment; however, if necessary, paper consent forms will be retained by the Principal Investigator in a secure, double-locked environment. Participants will be offered a copy of the informed consent form via email or by texting them a link to the form online.

